1.7.2 Acalabrutinib in CLL

As of 01 October 2015, acalabrutinib has been administered to > 800 participants in clinical studies, including subjects with hematologic malignancies, solid tumors, or rheumatoid arthritis, and participants who are healthy volunteers or with mild to moderate hepatic impairment. No SAEs have been reported in the hepatic impairment study or in the healthy volunteer studies. For more detailed information on the clinical experience for acalabrutinib, please refer to the Investigator Brochure.

This section briefly summarizes data from ACE-CL-001 (NCT02029443), an ongoing non-randomized, sequential group, dose-escalation Phase 1/2 study in subjects with relapsed/refractory or previously untreated CLL, Richter's syndrome, or prolymphocytic leukemia.

As of 01 October 2015, 60 subjects with relapsed CLL have been evaluated for tumor response based on International Working Group response criteria ([Hallek 2008](#)) as recently updated ([Cheson 2012](#)) to include PR with treatment-induced lymphocytosis (PRL). With a median follow up of 14.3 months, an ORR of 95% has been observed ([Byrd 2016](#)). Few subjects have had disease progression and no Richter's transformation has been observed in these subjects.

1.8 KEYTRUDA (PEMBROLIZUMAB)

Pembrolizumab (Keytruda [United States]), a humanized monoclonal antibody against the programmed death receptor-1 (PD-1) protein, has been developed by Merck & Co for the treatment of patients with cancer. Pembrolizumab is approved for treatment of patients with melanoma in several countries; in the United States and European Union it is approved for the treatment of adult patients with advanced (unresectable or metastatic) melanoma. Pembrolizumab has also been approved for treatment of patients with NSCLC in several countries; in the United States it is indicated for the treatment of patients with metastatic NSCLC whose tumors express PD-L1 as determined by an FDA-approved test and who have disease progression on or after platinum-containing chemotherapy. Patients with NSCLC and EGFR or ALK genomic tumor aberrations should also have disease progression on FDA-approved therapy for these aberrations prior to receiving pembrolizumab. For complete information on pembrolizumab refer to the KEYTRUDA package insert ([Appendix 6](#)) or to the Pembrolizumab Investigator Brochure. Serious adverse reactions associated with pembrolizumab are described in the package insert ([Appendix 6](#)) and also [Section 3.8.1](#) of this protocol.

1.9 BENEFIT/RISK

Acalabrutinib is a potent, orally administered small-molecule inhibitor of BTK. A PK/PD study has been completed with acalabrutinib in healthy volunteers (ACE-HV-001). The safety results showed no safety risk was identified in healthy subjects receiving 1 or 2 days of acalabrutinib \leq 100 mg. In the Phase 1/2 study of acalabrutinib in subjects with CLL, an ORR of 95% has been observed with a median follow-up of 14.3 months. In summary, the preliminary data suggest that acalabrutinib is well tolerated and has robust activity as a single agent in the treatment of subjects with CLL including those with 17p del.

The nonclinical and toxicology results of acalabrutinib suggest it may have an improved therapeutic window relative to ibrutinib; it may be more readily combined with other agents for the treatment of cancer. Based on the currently known toxicity profiles of acalabrutinib and pembrolizumab overlapping toxicities are not anticipated. Preliminary results in preclinical cancer models suggests a synergistic antitumor effect of BTK inhibition in combination with PD-1 blockade, which support evaluating the combination in clinical trials.

2.0 STUDY OBJECTIVES

2.1 PRIMARY OBJECTIVES:

- To characterize the safety profile of acalabrutinib and pembrolizumab in subjects with recurrent or metastatic NSCLC
- To determine the ORR of pembrolizumab monotherapy and the combination of acalabrutinib and pembrolizumab in subjects with recurrent or metastatic NSCLC

2.2 SECONDARY OBJECTIVES:

- To determine PFS in subjects treated with pembrolizumab monotherapy and the combination of acalabrutinib and pembrolizumab
- To evaluate the OS in subjects treated with pembrolizumab monotherapy and the combination of acalabrutinib and pembrolizumab

2.3 EXPLORATORY OBJECTIVES

- Determine the effects of acalabrutinib plus pembrolizumab on peripheral blood T cells and MDSCs
- Determine the PK of acalabrutinib alone and in combination with pembrolizumab
- Determine if any characteristics of peripheral blood T cells and/or MDSCs correlate with immune-mediated toxicities
- Determine if any characteristics of peripheral blood T cells and/or MDSCs correlate with response to acalabrutinib and pembrolizumab
- Determine if any baseline tumor characteristics correlate with response to acalabrutinib and pembrolizumab
- Evaluate the efficacy of adding acalabrutinib to pembrolizumab in subjects who progress on pembrolizumab monotherapy

3.0 STUDY DESIGN

This clinical trial is a Phase 2, multicenter, open-label, randomized study evaluating pembrolizumab monotherapy and the combination of acalabrutinib and pembrolizumab in subjects who have recurrent or metastatic NSCLC.

Subjects meeting the eligibility criteria for the study will be randomized 1:1 to one of the following arms:

Arm 1: Pembrolizumab 200 mg administered as an IV infusion every 3 weeks (Q3W)

Arm 2: Acalabrutinib 100 mg administered PO BID plus pembrolizumab 200 mg IV Q3W

Acalabrutinib treatment can continue for subjects who are tolerating therapy and not progressing. Pembrolizumab treatment is for 24 months from the date of first dose for subjects who are tolerating therapy and not progressing. Subjects who progress on the combination of pembrolizumab and acalabrutinib will discontinue study treatment while those with progression of disease in the pembrolizumab monotherapy arm will continue on pembrolizumab with the addition of acalabrutinib until a second disease progression or intolerance to therapy. For subjects who cross over to receive combination treatment, acalabrutinib treatment will begin at the next visit at which subjects are scheduled to receive pembrolizumab. The dose of acalabrutinib for these subjects will be determined based on the DLT review of Arm 2. Disease progression will be determined based on irRECIST guidelines ([Appendix 8](#) and detailed in [Section 3.11](#)).

[figure not shown]
Pembrolizumab treatment can end for subjects with confirmed CR if treatment has been administered for at least 24 weeks and 2 doses of pembrolizumab have been administered after confirmation of CR. Treatment on this protocol can continue for a minimum of 12 months after the last subject is randomized.

All subjects will have hematology, chemistry, and urinalysis safety panels performed at screening. Once dosing commences (Day 1), all subjects will be evaluated for safety, including serum chemistry, serum amylase and lipase, and hematology. PD and PK testing will be performed during the first few months of treatment. Radiologic tumor assessments will be completed at baseline and at ~6-week intervals during the trial. Subjects who discontinue study drug for any reason other than disease progression,

death, lost to follow-up, or withdrawal of consent will be followed for tumor assessment until disease progression or initiation of any other anticancer therapies, whichever comes first.

Refer to [Appendix 4](#) and [Appendix 5](#) for comprehensive lists of study assessments and their timing. The study schema is provided below ([Figure 3-1](#)).

Figure 3-1. Study Schema

Abbreviations: ACP-196 = acalabrutinib; BID = twice per day; DLT = dose-limiting toxicity; IV = intravenous; NSCLC = non-small cell lung cancer; Q3W = every 3 weeks.

* Acalabrutinib and pembrolizumab administration begin on the same day except for the first 6 subjects enrolled due to pharmacokinetic sampling. In the first 6 subjects, acalabrutinib will be administered on Day 1 of Week 1. On Day 2 of Week 1, the first pembrolizumab infusion will occur. When both are administered on the same day, acalabrutinib is administered first followed by the pembrolizumab infusion.

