3.11 TREATMENT AFTER INITIAL RADIOLOGIC PROGRESSION

RECIST 1.1 will be adapted to account for the unique tumor response characteristics seen with treatment of pembrolizumab. Immunotherapeutic agents such as

pembrolizumab may produce antitumor effects by potentiating endogenous cancer-specific immune responses. The response patterns seen with such an approach may extend beyond the typical time course of responses seen with cytotoxic agents and can manifest a clinical response after an initial increase in tumor burden or even the appearance of new lesions. Standard RECIST may not provide an accurate response assessment of immunotherapeutic agents such as pembrolizumab. Therefore, RECIST 1.1 will be used with the following adaptations:

- If radiologic imaging verifies initial disease progression, tumor assessment should be repeated ≥ 4 weeks later to confirm disease progression with the option of continuing treatment per below.
- If repeat imaging shows $< 20\%$ tumor burden compared to nadir, stable or improved previous new lesion (if identified as cause for initial disease progression), and stable/improved non-target disease (if identified as cause for initial disease progression), treatment may be continued / resumed.
- If repeat imaging confirms disease progression due to any of the scenarios list below, subjects will be discontinued from study therapy (except subjects who cross over to receive acalabrutinib in addition to pembrolizumab).

In determining whether or not the tumor burden has increased or decreased, site study team should consider all target lesions as well as non-target lesions (if needed, the tip sheet provided in the study binder can be used as a reference to assess lesions).

Scenarios where disease progression is confirmed at repeat imaging:

- Tumor burden remains $\geq 20\%$ and at least 5 mm absolute increase compared to nadir
- Non-target disease resulting in initial disease progression is worse (qualitative)
- New lesion resulting in initial disease progression is worse (qualitative)
- Additional new lesion(s) since last evaluation

In subjects who have initial evidence of radiological disease progression, it is at the discretion of the treating physician whether to continue a subject on study treatment until repeat imaging is obtained. This clinical judgment decision should be based on the subject's overall clinical condition, including performance status, clinical symptoms, and

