
irRC Overall Tumor Assessments
 
irCR, complete disappearance of all lesions (whether measurable or not, and no new lesions)
 
 Confirmation by a repeat, consecutive assessment no less than 4 weeks from the date first documented 
irPR, decrease in tumor burden $\geq 50\%$ relative to baseline
 
 Confirmed by a consecutive assessment at least 4 weeks after first documentation 
irSD, not meeting criteria for irCR or irPR, in absence of irPD
 
irPD, increase in tumor burden $\geq 25\%$ relative to nadir (minimum recorded tumor burden)
 
 Confirmation by a repeat, consecutive assessment no less than 4 weeks from the date first documented 	
2.4 irRC Overall Tumor Assessments
 
irCR, complete disappearance of all measurable and non-measurable lesions. Lymph nodes must decrease to $< 10\text{ mm}$ in short axis. Confirmation of response is not mandatory.
 
irPR, decrease of $\geq 30\%$ in TMTB relative to baseline, non-target lesions are irNN, and no unequivocal progression of new non-measurable lesions.
 
irSD, failure to meet criteria for irCR or irPR in the absence of irPD.
 
irNN, no target disease was identified at baseline and at follow-up the patient fails to meet criteria for irCR or irPD.
 
irPD, minimum 20% increase and minimum 5 mm absolute increase in TMTB compared to nadir, or irPD for non-target or new non-measurable lesions. Confirmation of progression is recommended minimum 4 weeks after the first irPD assessment.
 
irNE, used in exceptional cases where insufficient data exists.
 
irND, in adjuvant setting when no disease is detected.
	
The irRECIST overall tumor assessment is based on TMTB of measured target and new lesions, non-target lesion assessment and new non-measurable lesions.
 
The thresholds for irPR and irPD assessment are aligned with RECIST 1.1, and confirmation of response is not required.
 
An irPD confirmation scan may be recommended for patients with a minimal TMTB %-increase over 20% and especially during the flare time-window of the first 12 weeks of treatment, depending on the compound efficacy expectations, to account for expected delayed response.

CONCLUSIONS

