irRECIST criteria as outlined here introduce the needed clarifications and adjustments to irRC criteria and Nishino et al., 2013 publication to allow for treatment evaluations that better meet both investigators' and patients' needs and with that better reflect sponsors' demands for more reliable and reproducible study data in targeted immunotherapy in oncology studies. The main adaptation of the existing immune-response criteria lies in the assessment of all detected lesions. Unequivocal and substantial increase of non-target and new non-measurable lesions prevents irCR and may also lead to irPD. Reduction of the tumor burden in patients in an adjuvant setting may lead to irPR and such patients may therefore be enrolled in studies with response endpoints.

Clinical relevance of these adaptations needs to be confirmed.

SUMMARY AND ADDITIONAL GUIDANCE

1. TMTB: Baseline-selected target lesions and new measurable lesions should NOT be assessed separately. Measurements of those lesions should be combined into the Total Measured Tumor Burden (TMTB), and one combined assessment provided.
2. New Measurable Lesions: According to irRC a measurable new lesion has to be at least 5 mm x 5 mm to be selected as an index lesion. For bidimensional measurements this threshold was acceptable. In irRECIST, criteria for unidimensional lesion measurement apply to both target and new measurable lesions: a minimum 10 mm in the longest diameter for non-nodal lesions, and a minimum 15 mm in short axis for lymph nodes. Smaller lesions contribute to the non-target or new non-measurable tumor burden, but do not get measured.
3. irPR if no Target Lesions: If new measurable lesions appear in patients with no target lesions at baseline, irPD will be assessed. That irPD timepoint will be considered a new baseline, and all subsequent timepoints will be compared to it for response assessment. irPR is possible if the TMTB of new measurable lesions decreases by $\geq 30\%$ compared to the first irPD documentation.
4. irPR in Adjuvant Studies: irRECIST can be used in the adjuvant setting, in patients with no visible disease on CT/MRI scans. The appearance of new measurable lesion(s) automatically leads to an increase in TMTB by 100% and leads to irPD. These patients can achieve a response if the TMTB decreases at follow-up, as a sign of delayed response.

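### The protocol gives no reference scan for the second progression after crossover; read literally, a subject who crossed over on growth in measured tumour burden meets irPD again with an unchanged tumour

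*Protocol*

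**What the plan says.** - **Crossover rule.** Protocol Section 3.0: an Arm 1 subject with progression "will continue on pembrolizumab with the addition of acalabrutinib until a second disease progression or intolerance to therapy". The same paragraph adds: "Disease progression will be determined based on irRECIST guidelines", pointing to Appendix 8 and Section 3.11. The second progression has no separate definition.
- **Progression reference.** Appendix 8, item 2.4: "irPD, minimum 20% increase and minimum 5 mm absolute increase in TMTB compared to nadir, or irPD for non-target or new non-measurable lesions". Section 3.11 uses the same size test (20% "and at least 5 mm absolute increase compared to nadir"), and Table 4-1 refers to the smallest sum on study.
- **Response reference.** Appendix 8, item 2.4: irPR is a fall in TMTB of at least 30% from baseline.
- **Reset of the reference.** Appendix 8, summary item 3, is the only such rule: "That irPD timepoint will be considered a new baseline, and all subsequent timepoints will be compared to it for response assessment". It covers patients with no target lesions at baseline. Inclusion criterion 4 requires measurable disease, so it does not reach this trial's subjects.
- **Crossover schedule.** Appendix 5 has no tumour-assessment row and returns subjects to the Appendix 4 calendar.
- **Stopping and follow-up.** Section 3.12 stops treatment on confirmed progression while receiving both drugs. Section 3.0 continues tumour scans after treatment only for those who stopped for a reason other than progression (or death, loss to follow-up or withdrawal of consent).
- **Objective.** Section 2.3 lists as exploratory: "Evaluate the efficacy of adding acalabrutinib to pembrolizumab in subjects who progress on pembrolizumab monotherapy".

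**The concern.** A subject who crosses over on TMTB growth is, at that moment, already at least 20% and 5 mm above nadir. If the same nadir remains the reference, the next scan is tested against a line the subject has already crossed. No growth on the combination is needed to meet irPD, and a modest shrinkage may not be enough to escape it. Response is likewise measured from a baseline that predates the growth.

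Two things are at stake. One is the estimate of what acalabrutinib adds after progression on pembrolizumab: a tumour that stops growing, the plainest sign of disease control, would be recorded as a failure. The other is that the same undefined event ends treatment, so sites must either apply the literal reading or each devise their own.

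**Working it through.** **The plan's own illustration of the nadir rule.** Appendix 8, item 2.1, says that five new lesions of 10 mm make a 20% increase when nadir TMTB is 25 cm, and two do so at 10 cm. Check: 50/0.20 = 250 mm and 20/0.20 = 100 mm. Both reproduce, so the rule is being read as its authors meant it.

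**Inputs.** irPD: TMTB at least 1.20 × nadir and at least 5 mm above it. irPR: TMTB at most 0.70 × baseline. TMTB combines target lesions and new measurable lesions (Appendix 8, item 2.0). The protocol gives no tumour sizes for crossover subjects, so the values of k and the sizes below are assumptions shown over a range.

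**Formulas.** Let burden at crossover be k × nadir.
- The shrinkage from crossover burden must exceed 1 − 1.2/k to avoid a second irPD.
- If nadir is below 25 mm the 5 mm condition governs, and the figure becomes 1 − (nadir + 5)/(crossover burden).
- irPR, if nadir equals the original baseline, needs a fall of 1 − 0.7/k.

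| k | Shrinkage to exceed to avoid irPD | Fall needed for irPR (nadir = baseline) |
|---|---|---|
| 1.2 | 0% (any shrinkage) | 42% |
| 1.4 | 14% | 50% |
| 1.6 | 25% | 56% |
| 2.0 | 40% | 65% |

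For a small tumour (nadir 15 mm, crossover 30 mm, k = 2.0) the 5 mm condition gives 1 − 20/30 = 33% instead of 40%.

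**Example on the TMTB route.** Nadir 50 mm, crossover 65 mm (k = 1.3); the irPD line is 1.2 × 50 = 60 mm.
- Unchanged at 65 mm: +30% over nadir, irPD.
- Shrunk 5% to 61.75 mm: +23.5%, irPD.
- Shrunk 10% to 58.5 mm: +17%, not irPD.

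**Same subject, referenced to the crossover scan.** The progression line becomes 1.2 × 65 = 78 mm, so 65 mm is stable. A 30% response needs 0.7 × 65 = 45.5 mm. With the original baseline equal to nadir it needs 0.7 × 50 = 35 mm, a 46% fall from 65 mm.

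**Where nadir lies below baseline.** Baseline 100 mm, nadir 80 mm, crossover 110 mm. A next scan at 100 mm (9% smaller) is 100/80 = +25%, so irPD; the tumour must fall below 96 mm, a shrinkage of more than 12.7%. irPR needs 70 mm, a 36% fall, so the irPR column above is specific to nadir = baseline.

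**Non-target route.** Nadir 50 mm, crossover 54 mm (+8%), progression declared on non-target disease. The size criterion was never met. Section 3.11 asks of such lesions whether they have worsened, so unchanged disease is not progression.

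**The case against.** **The old nadir is a default, not a stated rule.** No sentence says that progression after crossover is judged against the pre-crossover nadir. The word second suggests a further event, and Section 3.12 can be read as progression arising on the combination. This stands: the defect is an unstated reference whose literal default misbehaves.

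**Section 3.11 does not itself declare the second progression.** A reader might infer that its test of whether burden remains 20% above nadir applies directly to the first scan after crossover. That section concerns confirmation of the initial progression, and it exempts crossover subjects from discontinuation at that point. The literal reading runs through Section 3.0 to the irPD definition in Appendix 8.

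**The problem is not universal.** A reader might infer that every crossover subject exceeds the reference by definition, or that stable disease after crossover is impossible. Neither is supported. Progression on non-target or new non-measurable lesions needs no 20% rise. On the TMTB route, at k = 1.4 with nadir equal to baseline, a shrinkage above 14% and below 50% is neither irPD nor irPR and so counts as stable.

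**The objective is exploratory and partly recoverable.** Section 3.11 says irRECIST data will be collected in the database. It allows continuation by exception after sponsor consultation, and Section 3.12 allows it when true progression is uncertain. An analysis plan could re-reference change to the crossover scan. It is therefore too strong to infer that the objective cannot be answered or that treatment must always end. The repair is still incomplete: an analysis plan cannot alter the stopping event, and once a subject stops for a nominal second progression, Section 3.0 requires no further scans.

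**Conclusion.** The point holds in limited form. The protocol ends crossover treatment at a second progression without saying what it is measured against. The only references it supplies make unchanged disease count as irPD for any subject who crossed over on TMTB growth. The shrinkage needed to escape runs from any amount at k = 1.2 to 40% at k = 2.0, subject to the 5 mm condition in small tumours. Post-crossover disease control, response and time to second progression are biased toward no effect.

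This rests on the literal reading, on assumed values of k, and on the TMTB route. How many of the up to 37 Arm 1 subjects would cross over by that route cannot be derived from the protocol. The randomised-arm endpoints do not use a post-crossover reference and are unaffected. Because the objective is exploratory and exceptions exist, this is a should-fix point rather than a must-fix one.

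**What to change.** **Post-crossover efficacy endpoints.** State that the last scan before the first acalabrutinib dose is the reference for response, disease control and progression, that nadir is counted from that scan, and that lesions already present on it are not new. Keep the original baseline and nadir for the randomised-arm endpoints.

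**Treatment-stopping event.** Reconcile Sections 3.0, 3.11 and 3.12 with Appendices 5 and 8 so that the reference for the second progression is stated. Which stopping rule to adopt is for the sponsor.

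**Cost.** A few sentences in an amendment and a case report form flag marking the reference scan; normally no extra imaging. The reference scan may be somewhat old by the first acalabrutinib dose, since crossover waits for the next pembrolizumab visit. Clinically unstable subjects need not have a confirmatory scan under Section 3.11; for them the first progression scan would serve.
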